It is unknown if in-hospital video education (with repeat viewing post-discharge as desired) that uses symbolic modeling and is aimed at enhancing recognition of and HF self-care response actions to new or worsening dyspnea, fatigue and edema danger signs, (a) *reduces all-cause and HF-related healthcare resource utilization (HCRU)*, (b) *improves perceptions of dyspnea and fatigue*, and (c) *improves self-efficacy for managing symptoms*. Learning the HCRU effects of

NCT-03657459

symbolic modeling video education that explains the most common HF danger signs (dyspnea, fatigue and edema) and provides practical actions to reduce danger signs is important, as the intervention is easy to deploy, uses standard HF self-care behavior expectations, and is practical to use in hospital and home environments.

It is important to learn the *time to the video intervention effect* on (a) HCRU outcomes and (b) perceptions of fatigue, dyspnea and self-efficacy for managing HF symptoms. The intervention may have an early effect (30-days) that wanes over time, have a steady effect over a 6-month period, or the effect may be slow to peak (i.e., 90 or 180 days) as patients may learn through a recognition and self-care action “trial and error” approach.

Finally, the video intervention effect on outcomes may differ based on *after hospital discharge viewing by patients and/or family supporters*, as repeated viewing and/or family supporter viewing of danger signs and HF self-care actions may facilitate *earlier recognition* of warning signs and/or *earlier or more accurate adherence* to HF self-care actions that lead to improved HCRU outcomes, lower perceptions of fatigue and dyspnea and improved self-efficacy for managing symptoms.

Study Purposes

The purposes of this study are to examine the effects of HF danger signs videos (1 each on dyspnea, fatigue and edema) that include 2 key features: (1) recognition of each danger sign and (2) common, simple, practical self-care actions known to reduce HF danger signs ([a] fatigue: recognizing that it may be due to dehydration and adhering to physical activity and exercise expectations; [b] dyspnea and edema: adhering to a low sodium diet and fluid intake limitations; [c] all 3: contacting a doctor when appropriate). Based on Bandura’s social cognitive theory symbolic modeling, video content is meant to increase self-efficacy for independently completing self-care actions when dyspnea, fatigue and/or edema are present.

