The following outcomes will be assessed:

PRIMARY

1. 30 ± 6 days *first occurrence* of post-discharge **HF-related** HCRU; defined as hospitalization, emergency department [ED] visits, death or cardiac transplantation/ ventricular assist device [VAD] implant-- individual components and combined),

SECONDARY:

2. 90- and 180-day ± 6 days *first occurrence* of post-discharge **HF-related** HCRU; defined as hospitalization, emergency department [ED] visits, death or cardiac transplantation/ ventricular assist device [VAD] implant-- individual components and combined),
3. 30-, 90- and 180-day ± 6 days *first occurrence* of post-discharge **all-cause** HCRU; defined as hospitalization, emergency department [ED] visits, death or cardiac transplantation/ ventricular assist device [VAD] implant-- individual components and combined),
4. 30-, 90- and 180-day ± 6 days *time to* first occurrence of **all-cause** and **HF-related** post-discharge HCRU (individual components and combined),
5. 30-, 90- and 180-day ± 6 days *total all-cause* post-discharge HCRU (individual components and combined);
6. 30-, 90- and 180-day ± 6 days *total HF-related* post-discharge HCRU (individual components and combined);

NCT-03657459

7. Change in *functional status* from baseline to 30-, 90- and 180-days \pm 6 days after hospital discharge,
8. Change in *dyspnea scores* from baseline to 30-, 90- and 180-days \pm 6 days after hospital discharge,
9. Change in *fatigue scores* from baseline to 30-, 90- and 180-days \pm 6 days after hospital discharge, and
10. Change in *self-efficacy for managing symptoms* from baseline to 30-, 90- and 180-days \pm 6 days after hospital discharge
11. Differences in primary and secondary outcomes (1-10) among *intervention-group participants*, after creating 3 sub-groups based on post-discharge video viewing ([a] total number of times videos were watched, [b] viewed by caregivers/family in the hospital, and [c] viewed by caregivers/family post hospital discharge.

Specific aims and hypotheses:

1. Determine the effects (and time to effects) of HF danger signs education on *first occurrence*, *time to first occurrence* and *total* all-cause and HF-related HCRU after hospital discharge: hospitalization, ED visit, death, cardiac transplantation or VAD.
2. Examine if functional status, dyspnea, fatigue and self-efficacy for managing symptoms scores change over time and the direction of change.

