3. Among intervention group participants, determine if post-discharge re-viewing of danger signs education by patients and/or viewing content by family supporters is associated with differences in HCRU, functional status, dyspnea, fatigue and self-efficacy for managing symptoms, including time to effects.

Hypothesis 1a: 30-day post-discharge HCRU will be lower or trend toward lower, and 90-, and 180-day *first occurrence*, and *total* HCRU will be lower in the HF video danger education group compared to the usual care group.

Hypothesis 1b: *Time to first* HCRU occurrence will be longer at 30-, 90- and 180-days in the HF video danger education group compared to the usual care group.

Hypothesis 1c: *Total* HCRU will be lower at 30-, 90- and 180-days in the HF video danger education group compared to the usual care group.

Hypothesis 2a: *Functional status* scores improve at 30-days and remain lower over time in the HF video danger education group compared to the usual care group.

Hypothesis 2b: *Dyspnea* scores improve at 30-days and remain lower over time in the HF video danger education group compared to the usual care group.

Hypothesis 2c: *Fatigue* scores improve at 30-days and remain lower over time in the HF video danger education group compared to the usual care group.

Hypothesis 2d: *Self-efficacy for managing symptoms* scores are higher at 30-days and remain higher over time in the HF video danger education group compared to the usual care group.

NCT-03657459

Hypothesis 3a: Repeat viewing of videos by patients, compared to 1-time viewing in-hospital and/or viewing of videos by family supporters/caregivers in hospital and/or post discharge, compared to viewing only by patients will be associated with *longer time to first HCRU and lower total HCRU*.

Hypothesis 3b: Repeat viewing of videos by patients, compared to 1-time viewing in-hospital and/or viewing of videos by family supporters/caregivers in hospital and/or post discharge, compared to viewing only by patients will be associated with *improved functional status* and *dyspnea and fatigue scores* (due to heightened awareness of danger signs, heightened recognition of worsening of danger signs)

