Hypothesis 3c: Repeat viewing of videos by patients, compared to 1-time viewing in-hospital and/or viewing of videos by family supporters/caregivers in hospital and/or post discharge, compared to viewing only by patients, will be associated with *higher self-efficacy for HF self-care actions* (due to symbolic modeling of self-care actions)

METHODS

Design: The study will use a 2-group, randomized, placebo-controlled, single blinded, design. Healthcare providers and unit nurses will be blinded to group assignment, but may learn about HF danger signs education if they enter the patients' room during intervention delivery or discuss the intervention prior to hospital discharge.

In brief, the research intervention involves 3 novel short videos (fatigue, dyspnea and edema) that will be viewed back-to-back by intervention group patients using a DVD player. Wellflix, Inc. videos are research-informed, use behavioral-modeling, are personally-tailored and are available 24/7 online. Patients will receive a handout sheet with the web address to view the videos after discharge and will be encouraged to view them with family members.

Sample (including sample size calculation) and Setting

A total of 732 patients will be enrolled (366 per group) and consist of adults with chronic HF (diagnosis \geq 2 months) who are hospitalized for acute decompensated HF within Cleveland Clinic Hospitals. This sample size includes a 10% attrition rate. Sample size was based on power calculations using 30-day first occurrence of HF-related HCRU (hospitalization, emergency department visit, mortality, cardiac transplantation or VAD). The current expected 30-day HF-related readmission rate is 20% among the control group. Allowing for other HCRU components, a control group HCRU rate of 28% is expected at 30 days. At 90 days, HCRU rate of 46% is expected in the control group. Sample size calculations were performed using SAS software (version 9.4; Cary, NC) and assume use of two-sided Pearson -chi square tests. With 329 patients in each group there will be 80% power to detect a 33% relative decrease (9.2% absolute decrease) in first occurrence of HF-related HCRU from a HCRU rate of 28% in the control group. With this sample size there would also be 85% power to detect a relative decrease of 25% (absolute decrease of 11.5%) from a control group event rate of 46% at 90-days. Allowing for 10% loss to follow-up, we will enroll 366 patients per group (732 total).

NCT-03657459

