Patient characteristics will be summarized overall and by randomized group using frequencies and percentages for categorical factors and means and standard deviations for continuous measures. First occurrence HCRU use (**all-cause and HF-related**) will be compared using Pearson chi-square tests. Time to first HFCU use will be summarized using Kaplan-Meier estimates, and compared using log-rank tests and Cox proportional hazards models. Total HCRU use will be compared using Poisson regression models. Linear mixed effect models will be used to evaluate trends in functional, dyspnea, fatigue, and self-efficacy measures over time and, if trends significantly differ, comparisons within time point will be performed. Secondary analyses will use similar methods to compare patients in the video group, stratified by video viewership, on the same outcomes. If appropriate, exploratory analyses will also be performed, comparing the above outcomes between treatment groups, adjusting for any patient characteristics that differ between randomized groups. Analyses will be performed using SAS software (version 9.4; Cary, NC), and an overall significance level of 0.05 will be assumed for all endpoints. Comparisons between the 3 subgroups of patients in the video group will use Bonferroni corrected significance criteria to preserve the overall error rate when making multiple comparisons.

Feasibility

The main campus of Cleveland Clinic has a high volume of HF discharges each year. Other hospitals in the system have moderate volumes of HF discharges, and are less likely to have patients who meet exclusion criteria due to enrollment in another research study or non-ambulatory NYHA FC IV (advanced) HF. Electronic medical records allow for review of data on events that occur in *all* system hospitals and regional medical practice ambulatory care sites; decreasing the need to rely on patient recall of HCRU.

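### Aim 1 asks when the video affects HCRU, but no planned HCRU analysis estimates or tests the timing of the effect

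*Combined protocol and SAP*

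**What the plan says.** The Introduction makes the timing of the effect on HCRU a question for the trial and sets out rival patterns: "The intervention may have an early effect (30-days) that wanes over time, have a steady effect over a 6-month period", or a benefit that peaks late, at 90 or 180 days. Specific aim 1 repeats the question for first occurrence, time to first occurrence and total HCRU.

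Secondary outcome 4 (Study Purposes) is "time to* first occurrence of all-cause and HF-related post-discharge HCRU" at 30, 90 and 180 days. Hypothesis 1b says that this time "will be longer at 30-, 90- and 180-days in the HF video danger education group". The Analyses section plans Kaplan-Meier estimates, compared with "log-rank tests and Cox proportional hazards models", and states that "an overall significance level of 0.05 will be assumed for all endpoints". For HCRU it describes no comparison within separate intervals, no treatment-by-time term and no check of proportional hazards. Models of trend over time are planned only for functional status, dyspnea, fatigue and self-efficacy scores.

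**The concern.** The 30-day window lies inside the 90-day window, and both lie inside the 180-day window. A significant result at 90 or 180 days can come wholly from the first month. A single Cox hazard ratio takes the effect as constant, and a constant effect is only one of the patterns that the Introduction leaves open. The first-occurrence comparisons (outcomes 2 and 3) and the total-HCRU comparisons (outcomes 5 and 6) are cumulative in the same way, so they do not fill the gap.

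At stake is how the secondary results are read. A significant 180-day result could be reported as sustained benefit when the effect stopped at day 30. A late benefit could be diluted by a first month without effect.

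**Working it through.** **Inputs from the documents** (Sample and Setting; Analyses). Two-sided 0.05; the power calculations "assume use of two-sided Pearson -chi square tests". For the control arm, "a control group HCRU rate of 28% is expected at 30 days", and 46% at 90 days. Video arm: 28% − 9.2% = 18.8% and 46% − 11.5% = 34.5%. 329 per arm after loss, 366 enrolled. The 46% is not labelled HF-related; it is read here as the same endpoint as the 28%.

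**Assumption.** The documents give no 180-day control rate. 55%, 60% and 65% are used.

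**1. The plan's own figures.** Power = Φ[(difference − 1.96 × SE₀)/SE₁], with SE₀ pooled and SE₁ unpooled.
- 30 days: (0.092 − 1.96 × 0.03301)/0.03281 = 0.832, power 79.7% (stated 80%).
- 90 days: (0.115 − 1.96 × 0.03824)/0.03797 = 1.055, power 85.4% (stated 85%).
- Enrolment: 329/0.90 = 365.6, so 366. The figures reproduce.

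**2. Overlap of the windows.** First events expected by day 30: 329 × (0.28 + 0.188) = 154. By day 90: 329 × (0.46 + 0.345) = 265. The share already counted by day 30 is 154/265 = 58%. The correlation of the 30- and 90-day log-rank statistics is about √0.581 = 0.76.

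**3. Hazard ratios implied by the plan's rates.**
- Days 0-30: ln(0.812)/ln(0.72) = 0.634.
- Days 31-90: ln(0.655/0.812)/ln(0.54/0.72) = 0.747.

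**4. Simulation.** Piecewise-constant hazards, 329 per arm, 3,000 trials per setting, hazard ratio 0.634 where the video acts and 1.0 elsewhere. Entries are the percentage of trials significant in favour of video; ranges run over the settings with 55% to 65% at day 180.

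| True effect | 0-30 | 0-90 | 0-180 | 31-90 only | 91-180 only |
|---|---|---|---|---|---|
| Days 0-30 only | 79-81 | 55-56 | 41-46 | 2-3 | 2-3 |
| Steady | 80 | 95-96 | 98-99 | 63-64 | 41-68 |
| After day 30 only | 3 | 25-27 | 45-67 | 59-62 | 37-66 |

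Mean cumulative hazard ratios at 30, 90 and 180 days:
- early only: 0.64, 0.78, 0.82-0.84
- steady: about 0.63 throughout
- late only: 1.00, 0.85-0.86, 0.78-0.82

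At a 55% control rate, early-only and late-only effects reject almost equally often at 180 days (46% and 45%). Repeat early-only runs gave about 53% to 55% at 90 days and 40% to 46% at 180 days. The 90-day figure cannot depend on the assumed 180-day rate, so its spread is simulation error: the standard error is √(0.55 × 0.45/3,000) = 0.9 points.

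**5. Power of a direct test of timing.** To compare days 0-30 with days 31-180, z = |ln(HR₁/HR₂)|/√(4/E₁ + 4/E₂), with E the events in each period, and power = Φ(z − 1.96).
- Early only, 55% at day 180: E₁ = 154, E₂ = 189; z = 0.456/0.217 = 2.10, power 56%.
- Late only, 65% at day 180: E₁ = 184, E₂ = 209; z = 0.456/0.202 = 2.25, power 62%.
- Across all settings: 54% to 62%.
- The contrast in step 3 (0.634 against 0.747; 154 and 111 events): z = 0.164/0.249 = 0.66, power about 10%.

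A joint test over three periods (two degrees of freedom) has the same noncentrality when the two later hazard ratios are equal, so its power is lower still.

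**The case against.** A reader might infer that the planned analyses can say nothing about timing and that aim 1 must go unanswered. The documents do not support that. Kaplan-Meier estimates are planned, and they show where the curves separate or converge. The cumulative hazard ratios in step 4 also drift differently under the three patterns. This stands, but it is description: no planned analysis puts an estimate or an interval on the change in effect.

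A reader might also take the late rejections in step 4 for false positives. They are not. Under the early-only pattern the cumulative risk really is lower: 1 − 0.812 × 0.75 = 39.1% against 46% at day 90, and 49% to 61% against 55% to 65% at day 180. Hypotheses 1a and 1b concern these cumulative quantities. Only the added inference of a continuing effect would be wrong, and the documents do not commit to it.

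Nor do the documents say that the effect is expected to vary; a steady effect is one of the possibilities they list. The Analyses section also does not say outright that data are cut at each horizon. That is the natural reading of outcome 4 and hypothesis 1b.

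The strongest objection is to the remedy. The period test is weak (step 5), and hazard ratios after day 30 compare patients who are still event-free, who are no longer strictly the randomized groups. Under an assumed gamma frailty (variance 0.5 to 2, not from the documents), a constant individual effect gives period hazard ratios of 0.63, then 0.67-0.76, then 0.69-0.87: apparent waning where there is none. This stands and limits how the added model may be read. It does not make the cumulative tests informative about timing.

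**Conclusion.** The point holds in a limited form. Timing of the effect on HCRU is a stated aim, and no planned HCRU analysis formally estimates or tests it. An effect that ends at day 30 yields a significant log-rank result in about 55% of trials at 90 days and about 40% to 46% at 180 days, so such a result is not evidence that the effect continues.

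The sizes rest on 329 per arm with complete follow-up, the plan's 28% and 46%, hazards constant within each period, and the assumed 55% to 65% at day 180. The 30-day primary endpoint, its chi-square test and the sample size are untouched. This is a cheap improvement to the secondary analyses, not a flaw in the trial's main conclusion.

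**What to change.** Keep the cumulative analyses for hypotheses 1a and 1b. Add to the Analyses section, as a secondary analysis, one Cox model to 180 days with separate hazard ratios for days 0-30, 31-90 and 91-180, 95% confidence intervals and a treatment-by-period test. Name in advance the contrast to be tested, for example days 0-30 against the later periods combined. State that a continuing effect will not be inferred from the cumulative tests alone.

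Write the limits into the same paragraph:
- The period contrast has about 54% to 62% power even for a wholly early or wholly late effect, so a non-significant result is not evidence of a steady effect.
- Hazard ratios after day 30 compare event-free survivors and can show apparent waning through selection. They are to be read mainly as estimates, beside the Kaplan-Meier curves.

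The cost is a paragraph of text and one model on data already collected, with no extra patients or visits. It should be fixed before outcome data are seen, so that the periods are not chosen afterwards.

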The fatigue and dyspnea video's will be viewed back-to-back and the edema video will be added for patients with a history of edema. There are 4 versions of each video: (1) based on race (Caucasian and African-American) and sex (male and female)—to promote symbolic modeling— by patients who look like video models (as stated in the introduction). Scripts for each video were developed jointly by [name], Director of Media and Education for Wellflix, Inc. and [name] PhD, principal investigator and clinical nurse specialist in HF. Content includes recognition and assessment of fatigue, dyspnea and edema and specific actions to take to reduce the danger signs or prevent worsening (dietary sodium and/or fluid restriction, physical activity/exercise and contacting the doctor).

Overall video viewing time for all 3 videos is 9:50 minutes; the fatigue and dyspnea videos that all intervention patients will view are 6:50 minutes:

- *Fatigue* is 2:20 minutes + end text list= 3:00 minutes;

NCT-03657459

- *Dyspnea* is 1:40 minutes + dyspnea “yes” or “no” management (2 options; patient selects the option that matches current status) = 3.50 minutes
- *Edema* is 2:40 minutes + end text list= 3:00 minutes;

During hospitalization, videos will be loaded into an iPAD and will be viewed through the iPAD.

Patients have an opportunity to view videos post-discharge as desired and able. *Post discharge*, videos can be in 2 ways: (1) via the Wellflix, Inc. site at www.wellflix.net/DangerSignsCC or (2) by DVD player (DVD created by Wellflix, Inc for this research), for patients who have DVD player capability and prefer this method.

NOTE, at/after 180-day follow up data are collected, *usual care group* patients will be offered access to Wellflix, Inc. videos used in this research study via mailing of a handout sheet developed specifically for them (that contains the web address and a note of encouragement to view the videos.

Outcomes and Measurement

HCRU. Includes all-cause and HF-related hospitalization, ED visit, death, cardiac transplantation, or VAD placement at 30-, 90-, and 180-days \pm 6 days in both groups. Data will be retrieved from medical records when available or via telephone call to patients.

- Patients will receive a calendar to keep track of HCRU events in-between phone calls.
- Research nurses will use a case report form to record HCRU events

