After completing baseline paperwork, patients will be randomly assigned to the usual care or usual care plus HF danger signs video education group using block randomization; with blocks of 20, to decrease the influence of external factors that could alter outcomes. The randomization assignment will be made by a QHS statistician.

After randomization to groups:

- Intervention group patients will receive usual hospital care and also, HF danger signs education via iPad by research personnel. Danger signs education can be administered at the time of enrollment. There is no need to wait until day of discharge, since HF danger sign messages are not individualized and discharge is a very busy time. Immediately prior to discharge, patients' focus may be on preparing to leave the hospital and not on education about HF, especially if patients believe that they have accurate perceptions of HF danger signals, even though in previous research, most subjects did not.
- Usual care group patients will be educated by their healthcare providers (including nurse/other caregivers). Education may include Elsevier HF videos that are shown on Cleveland Clinic hospital televisions.

A research nurse will use telephone calls or mailing methodologies to have the following 4/5 tools (40/43 items in total for usual care and intervention groups, respectively) completed at 30 ± 6 days: functional status, dyspnea, fatigue, self-efficacy for managing symptom and video watching experiences. Administration of functional status, dyspnea, and fatigue questionnaires will be randomly ordered (counterbalanced). The intervention-only group survey on video watching experiences will be administered last. It is expected that data collection will take ~ 10 minutes or less.

A research nurse will review EMRs of enrolled patients after the index (baseline) hospital discharge and at 30-, 60-, 90- and 180-days (± 6 days) for HCRU events.

- If not found in the EMR, telephone calls will be made to gather data.
- At baseline, research nurses will obtain home telephone number and the telephone number of a close relative or friend that can provide patient contact information, as needed.

NCT-03657459

Analyses

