The HF danger signs videos provide information that patients should understand, but that may not have been explicitly explained previously; therefore, it may be considered an extension of usual care education. Ideally, no new information is presented; as patients receive content about HF signs and symptoms and HF self-care actions via CC video education (in-hospital, when attentive) and via the HF handbook, which is sent home and can be re-given in ambulatory care. Danger signs video content was based on symbolic modeling; and has a *repeatable format*, if patients in the intervention group choose to utilize the on-line 24/7 viewing option post discharge. Patients do not need to be able to read and if they are forgetful or have mild memory impairment that was not documented at enrollment, they can replay videos multiple times.

Research personnel from the Office of Nursing Research and Innovation will recruit subjects, apply the intervention and collect data (at all sites). The main campus has multiple research projects in place, led by physicians, myself and other RNs. Research team personnel are accustomed to working with cardiology research nurses, as needed, to ensure patients are not approached for more than 1 research study.

Instruments that will be completed at baseline may be self- or research nurse-administered (patient demographics, HF characteristics, danger signs [dyspnea and fatigue], functional status and self-efficacy for managing symptoms). The patient demographics and HF characteristics instruments have been used many times in previous HF research and are short, simple and quick

NCT-03657459

to complete. Patients may become fatigued when completing baseline data collection forms; however, all 6 tools have only 71 items (in total) and all tools are short (12 or less items; each one should take about 3 minutes to complete).

- At baseline, all 6 tools should take and take under 20 minutes to complete. In previous research, patients were NOT burdened by data collection that included similar length instruments.
- At follow-up, telephone calls are only made when HCRU data is not available in medical records at 60-, 90- and 180-days. Data obtained from electronic medical records is consistently present, minimizing the occurrence of missing data.

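### Events outside the hospital system may be missed: patients are asked about HCRU only as a fallback to the EMR, and the trigger for asking is undefined

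*Combined protocol and SAP*

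**What the plan says.** All references are to the combined protocol and SAP.

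- **Source of HCRU data.** Outcomes and Measurement treats record and telephone as alternatives: "Data will be retrieved from medical records when available or via telephone call to patients". Research nurses enter events on a case report form.
- **Schedule and trigger.** Data Collection: "A research nurse will review EMRs of enrolled patients after the index (baseline) hospital discharge and at 30-, 60-, 90- and 180-days", followed by "If not found in the EMR, telephone calls will be made to gather data".
- **Limit on calls.** Feasibility: "telephone calls are only made when HCRU data is not available in medical records at 60-, 90- and 180-days". Day 30 is not in that list.
- **Reach of the EMR.** Feasibility: "Electronic medical records allow for review of data on events that occur in *all* system hospitals and regional medical practice ambulatory care sites". No outside hospital is mentioned, and the same section treats EMR data as reliably present.
- **Calendar.** Outcomes and Measurement: "Patients will receive a calendar to keep track of HCRU events in-between phone calls". No rule says that it is collected from, or read out by, every patient.
- **30-day contact.** Data Collection plans a telephone or mail contact with both groups for "4/5 tools (40/43 items in total for usual care and intervention groups, respectively").

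**The concern.** The primary endpoint and outcomes 2 to 6 all depend on finding every hospitalization, ED visit, death, transplant and VAD. An EMR can be complete for care inside the system and silent about an ED visit elsewhere. If a silent record is taken as an event-free patient, that visit becomes a non-event. If a recorded in-system event ends the search, an outside event that came earlier, or in addition, is lost.

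Three things are at stake: the accuracy of time to first event and of total counts; under one reading, the power of the primary test; and the comparability of the arms. On the last, the Design section states blinding for healthcare providers and unit nurses only, and Feasibility has the same research personnel apply the intervention and collect the data. An undefined trigger leaves the decision to call with staff for whom no blinding is stated.

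**Working it through.** **1. The two readings of the trigger.** *Not found* in the Data Collection sentence can mean either of two things.

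| Patient | Reading A: no HCRU event found | Reading B: no EMR data found |
|---|---|---|
| EMR present, no event in it; outside HF event | Called; event can be captured | Not called; counted as event-free |
| In-system HF event; earlier or additional outside event | Not called; primary status correct, but time to first event or total may be wrong | Same |
| In-system non-HF event only; outside HF event | Unclear whether called; the HF event may be lost | Not called; HF event lost |

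The second row fails on both readings and touches outcomes 4 to 6. The first row affects the primary endpoint, on Reading B only. The third row is a residual gap in the primary endpoint even on Reading A.

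**2. What the 30-day questionnaires contain.** Duke Activity Status Index 12 + dyspnea 10 + fatigue 10 + self-efficacy 8 = 40 items. The intervention group adds the 3-item viewing survey: 40 + 3 = 43. These totals use up the stated items, so no HCRU question is among the patient questionnaires.

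**3. The plan's own power.** Inputs from the Sample section: control rate 28%, relative decrease 33%, 329 per group, two-sided Pearson chi-square. The Analyses section gives alpha 0.05. The video-arm rate is 0.28 × 0.67 = 0.1876. With p̄ the mean of the two rates,

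power = Φ{ [ |p1 − p2|√n − 1.960·√(2p̄(1 − p̄)) ] / √(p1(1 − p1) + p2(1 − p2)) }.

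Putting the numbers in: (0.0924 × 18.138 − 1.960 × 0.5986) / 0.5950 = 0.845, and Φ(0.845) = 80.1%. The stated 80% is reproduced. For 46% vs 34.5% at 90 days the same formula gives 85.4%, matching the stated 85%.

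**4. Reading B, equal loss in both arms.** Multiply both rates by the share captured. The shares are assumptions, because the documents give none.

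| Missed (assumed) | Observed 30-day rates | Difference | 30-day power | 90-day power |
|---|---|---|---|---|
| 0% | 28.0% vs 18.8% | 9.2 points | 80.1% | 85.4% |
| 10% | 25.2% vs 16.9% | 8.3 points | 74.5% | 79.0% |
| 20% | 22.4% vs 15.0% | 7.4 points | 68.2% | 71.5% |
| 30% | 19.6% vs 13.1% | 6.5 points | 61.2% | 63.2% |

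The relative risk stays at 0.67 throughout; the absolute difference and the power shrink.

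**5. Unequal loss (assumed).** Observed relative risk = 0.67 × (share captured in video arm / share captured in control arm).

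- Control 90%, video 85%: 0.67 × 0.85/0.90 = 0.63, so the benefit looks larger than it is.
- Control 85%, video 90%: 0.67 × 0.90/0.85 = 0.71, so the benefit looks smaller than it is.

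**The case against.** The strongest reply is that Reading A is the natural one. The sentence before the trigger has the nurse reviewing the EMR for HCRU events, so what is not found is most simply an event, and every patient without one is called. A patient with an in-system HF event already counts for a yes/no endpoint, so the primary test loses little. The Feasibility limit on calls does not name day 30. The calendar, the up to three calls mentioned in the inclusion criteria and the separate HCRU case report form all suggest that calls were meant to gather HCRU. Using the EMR first is also a reasoned choice, made to rely less on patient recall. All of this stands, and it confines the effect on primary power to Reading B.

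A reader might infer three stronger things that the documents do not support.

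- **That outside events are certainly missed.** Reading A would catch most outside first events.
- **That HCRU goes unasked at 30 days.** The 40-item count shows only that HCRU is not in the questionnaires. It could be asked on the same call and put on the case report form. The text simply does not require it of every patient.
- **That the video arm could gain a false claim of benefit through better in-system capture.** No passage says that the advice to contact a doctor steers patients to in-system care. If it did, more control events would be missed and the video would look worse. With no true effect, 10% missed in the control arm only (25.2% vs 28%, 329 per arm) gives a rejection rate of 12.8%: about 12.6% false harm and 0.3% false benefit. A gap of 10% against 0% is itself an extreme assumption.

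The reply does not deal with the patient who has an in-system event and is not asked about outside events. Neither the calendar nor the case report form carries a rule that closes that gap.

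**Conclusion.** The point holds as a risk, not as an established loss. On either reading of the trigger, no passage requires that a patient with an in-system event be asked about outside events, so time to first event and total HCRU can be wrong by an amount the documents do not allow one to estimate. The binary 30-day primary endpoint is largely protected if *not found* means no event, apart from patients whose only in-system event is not HF-related.

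Only if it means no record does primary power fall: to 75%, 68% or 61% for an assumed 10%, 20% or 30% of events missed equally in both arms. Bias from unequal capture is possible in either direction, and the documents give no basis for choosing one. The planned sample size is correctly calculated and need not change. This is a cheap improvement in ascertainment, not a fatal flaw.

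**What to change.** 1. Reconcile Outcomes and Measurement, Data Collection and Feasibility so that they give one rule for when patients are called, including at day 30, and define *not found*.
2. At the 30-day telephone or mail contact already planned for both groups, ask every patient the same scripted HCRU question, answered from the calendar, whatever the EMR shows. Record the answer on the HCRU case report form. This also removes discretion over whom to ask.
3. Collect the calendar in the same way from all patients at 90 and 180 days.
4. Report a sensitivity analysis restricted to EMR-confirmed events.

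Cost: about a minute of extra burden per patient, and postage. The main downside is self-report from patients who know their group, with events whose HF-relatedness may not be confirmed without outside records. The EMR-confirmed analysis shows how far the result depends on those events.
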